#### 5.3 Concomitant Medications/Therapy

The Investigator may use any medical treatment that is judged appropriate and beneficial to the subject. All medications that are considered necessary for the subject's welfare may be used at the Investigator's discretion. Documentation of all medications used for ocular indications by the subject during this study will be recorded in the subject's source document and applicable CRFs.

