# 3.2.1.2 Exclusion Criteria

This study will include subjects who do not meet the following criteria:

- 1. Participation in a clinical trial within 30 days prior to entry into this study and/or during the period of study participation,
- 2. Previous intraocular or corneal surgery in either eye, including refractive surgery (e.g., LASIK),
- 3. Progressive sight threatening disease or other previous or current ocular conditions, other than myopia, that may predispose for future complication (e.g., diabetic retinopathy, pseudoexfoliation, retinal detachment, ocular hypertension or glaucoma, clinically significant corneal disease (Fuchs, keratoconus, herpes simplex or zoster keratitis), retinal vascular disease, cataract, etc.) in either eye,
- Low/abnormal corneal endothelial cell density (ECD) according to recommendations in ISO-11979-10 (Tab. A.1),
- 5.
- 6. Amblyopia,
- 7. Presence of active or history of chronic inflammation in either eye (e.g., scleritis, uveitis, etc.),
- 8. Clinically significant irregular astigmatism in either eye, as determined by the Investigator,
- 9. Serious (i.e., life threatening), acute, chronic or systemic, non-ophthalmic disease or illness that would increase the operative risk, confound the outcome(s) of the study or which may preclude study completion (e.g., immunocompromised, connective tissue disease, clinically significant atopic disease, uncontrolled diabetes, insulin dependent diabetes, etc.),
- 10. Use of topical steroids at time of implantation,
- 11. Systemic or topical medication, other than prescribed study medications (e.g., systemic corticosteroids, anti-metabolites) that may confound the outcome or increase the risk to the subject,
- 12. Allergy to anesthetics or other postoperative medications required in this study,

- 13. Subject who is pregnant, plans to become pregnant, or is lactating during the course of the study, or has another condition associated with the fluctuation of hormones that could lead to refractive changes,
- 14. Subjects who, in the judgment of the Investigator, present any emotional, physiologic, or anatomical condition which may preclude participation in this study or provide an inappropriate landscape for the intended study treatment.

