#### 6.3 Reporting

#### 6.3.1 On-Site Expedited Reporting

The Investigator is obligated to report the following to the Sponsor within 24 hours of becoming aware of the event to ensure the safety of all participants in the study and to meet regulatory reporting requirements:

- all SAEs, regardless of relationship to study device or study protocol
- all **non-serious AEs** determined to be related to the study device (ADE)

- all device deficiencies that do not result in one of the above reportable events
- all secondary surgical interventions (removal, replacement or repositioning) involving the study lens

In addition, the following events are to be reported to the Sponsor as SAEs in this study:

- endophthalmitis
- pupillary block
- retinal detachment
- stromal thinning/corneal melting
- ≥2 lines BCDVA loss not secondary to any underlying condition after 3 months postoperative

All SAEs/ADEs and device deficiencies will be reported via the eCRF. The required information will be sent to the safety department of the CRO and the Sponsor automatically. Telephone, fax and e-mail can be used for initial reporting if there are difficulties accessing the eCRF. The contact details of the safety department of the CRO are:

All SAEs will be reported by the CRO on behalf of STAAR Surgical to the Competent Authorities of the involved countries according to the EU regulations and the national legislations.

The Sponsor is to report a SAE or a new finding to it which indicates an imminent risk of death, serious injury, or serious illness and that requires prompt remedial action for other subjects or a new finding to it to the regulatory authority immediately but not later than 2 calendar days of awareness of the event.

The Sponsor is to report any other SAE or a new finding/update to it immediately, but not later than 7 calendar days following the date of awareness of the event.

In addition, the CRO will report SAEs to the responsible EC without undue delay, if applicable according to national regulations. The CRO is responsible for checking what reporting procedures are applicable for his/her EC regarding SAEs and final report of the outcome of the study and to comply with such reporting procedures during the study period.

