# 7.1 Hypothesis

The implant procedure is defined as successful if the responder rate is equal to or greater than 75%. The corresponding statistical hypothesis is therefore as follows:

H 0 (null hypothesis):	$\pi < 0.75$

Ha (alternative hypothesis):  $\pi \ge 0.75$ 

where  $\pi$  is the true proportion of eyes that achieve the performance endpoint (i.e. UCNVA of Snellen equivalent 20/40 or better at 40 cm) at 6 months after implantation (6-month responder rate).

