#### 7.2 Study Endpoints

#### 7.2.1 Performance Endpoints

The primary performance endpoint is defined as achievement of monocular UCNVA of Snellen equivalent 20/40 or better at 40 cm at Visit 5 (6 months after implantation) in equal to or greater than 75% of implanted eyes (responder rate).

Fleming's two-stage design was used, which enables early termination of the study at an interim analysis for futility or performance. Here, an interim analysis will be performed with the results obtained from 27 subjects (54 eyes). If there are 43 or less responses, the trial will be stopped for futility since the likelihood of still obtaining a significant result is too low to continue the study under ethical considerations. If there are 48 or more responses observed at the interim analysis, the trial will be stopped and the null hypothesis rejected as enough statistical evidence has been accrued to determine that, within the certainty of the controlled one-sided type I error probability of 2.5%, the true responder rate is greater or equal to 75%.

Otherwise, 16 additional patients (32 eyes) will be recruited for a total of 43 patients (86 eyes). The null hypothesis will be rejected if 73 or more responses are observed among the 86 eyes. This design yields a one-sided type I error probability of 2.5% and a power of 80% if the true response rate is 87.5%.

Secondary performance endpoints include the following:

- Percentage of implanted eyes achieving monocular UCNVA of Snellen equivalent 20/40 or better at 40 cm at Visit 3 and 4 (1 and 3 months after implantation respectively)
- Change from baseline in monocular uncorrected intermediate visual acuity (UCIVA) at 80 cm at postoperative Visit 3, 4 and 5
- Change from baseline in monocular UCNVA at 40 cm at postoperative Visit 3, 4 and 5
- Change from baseline in monocular distance corrected intermediate visual acuity (DCIVA) at 80 cm at postoperative Visit 3, 4 and 5
- Change from baseline in monocular distance corrected near visual acuity (DCNVA) at 40 cm at postoperative Visit 3, 4 and 5
- Change from baseline in binocular UCNVA at 40 cm at postoperative Visit 3, 4 and 5

There are no prespecified performance targets for secondary performance endpoints. 95% confidence limits will be calculated for all secondary performance endpoints.

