# 7.3 Sample Size

Fleming's two-stage design was used to optimize the sample size while allowing for early termination of the trial for futility or performance. It is expected that 90% of eyes will achieve the performance endpoint and the sample size was therefore conservatively determined based on an 87.5% responder rate.

Based on Fleming's two-stage design, 27 subjects (54 eyes) will be enrolled prior to the interim analysis. In case the study is not terminated due to futility or reaching the performance endpoint, an additional 16 subjects (32 eyes) will be enrolled for a total of 43 patients (86 eyes). To allow for 10% attrition over 6 months, a total of 48 subjects (96 eyes) will be enrolled for assessment of the primary and secondary performance endpoints and the primary safety endpoint in case the study is not terminated after the first stage.

This design yields a one-sided type I error probability of 2.5% and a power of 80% if the true response rate is 87.5%.

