#### **Full Analysis Set:**

The FAS contains the data of each eye in the SES for which data has been collected for the primary performance endpoint.

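### The primary endpoint has no rule for eyes that reach 20/40 near only after a lens exchange, a refractive procedure or a pupil-constricting drop, so by default they count as responders

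*Combined protocol and SAP*

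**What the plan says.** **Endpoint.** Section 7.2.1 sets the primary endpoint as "achievement of monocular UCNVA of Snellen equivalent 20/40 or better at 40 cm at Visit 5 (6 months after implantation") in at least 75% of implanted eyes. It attaches no condition to what was done to the eye in the meantime.

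**Analysis sets.** In 7.5, "The FAS contains the data of each eye in the SES for which data has been collected for the primary performance endpoint". The per-protocol set drops eyes with major deviations, and 7.5 leaves the classes of deviation to the SAP. The text available contains no such classes.

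**Treatment after surgery.** Section 5.3 states: "The Investigator may use any medical treatment that is judged appropriate and beneficial to the subject". It also requires ocular medications to be recorded, but gives the record no analysis consequence. Exclusion criterion 11 (3.2.1.2) shows that the sponsor had the issue in mind: it bars "Systemic or topical medication, other than prescribed study medications (e.g., systemic corticosteroids, anti-metabolites) that may confound the outcome" or increase risk. It is an eligibility criterion and says nothing about endpoint status.

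**Lens surgery.** Section 4.3 supplies a supplemental lens for each eye. Section 6.3.1 requires expedited reporting of "all secondary surgical interventions (removal, replacement or repositioning) involving the study lens". Section 3.2.3 lists explant among the reasons for which a subject may be discontinued, at discretion.

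**Corneal enhancement.** Corneal surgery before entry is excluded. Enhancement after implantation is neither mentioned nor prohibited.

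**The concern.** Uncorrected near acuity responds directly to refraction and pupil size. A smaller pupil lengthens depth of focus, which is also the effect attributed to the lens. If an eye misses 20/40 with its implanted lens and passes after an added intervention, the success belongs at least partly to that intervention. With no control arm, such a gain has nothing to cancel against, and all of it is credited to the device.

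The decision is a raw count against fixed cut-offs, so a very small number of eyes can matter. If the status of these eyes is not fixed in advance, it may also have to be settled once the count is known to be near a boundary.

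**Working it through.** **Inputs from the plan**
- Null rate 75% (7.1): "The implant procedure is defined as successful if the responder rate is equal to or greater than 75"%.
- Stage 1 (7.2.1): "an interim analysis will be performed with the results obtained from 27 subjects (54 eyes"). Stop for futility at 43 or fewer responders; stop for success at 48 or more.
- Stage 2 (7.2.1): 32 more eyes. Success at 73 or more of 86.
- Stated properties (7.3): "This design yields a one-sided type I error probability of 2.5% and a power of 80% if the true response rate is 87.5"%.

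**Formula.** Treat eyes as independent, as the plan does, with X1 ~ Bin(54, p) and X2 ~ Bin(32, p):

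P(success) = P(X1 ≥ 48) + Σ P(X1 = x) · P(X2 ≥ 73 − x), summed over x = 44 to 47.

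**The plan's own figures**
- p = 0.75: 0.0096 + 0.0136 = 0.0232. This is within the stated 2.5%; it is not exactly 2.5% because counts are discrete.
- p = 0.875: 0.4799 + 0.3372 = 0.8171, against the stated 80%.
- Enrolment: 43 / (1 − 0.10) = 47.8, so 48 subjects.

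The design figures reproduce.

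**Effect of counting these eyes as responders.** Let q be the share of all eyes that respond only because of an added intervention, and set the unaided rate at exactly 75%, so p = 0.75 + q. The documents give no frequency for exchange, enhancement or drop use, so every q is an assumption.

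| q | Eyes of 86 (86 × q) | Observed rate p | P(success) |
|---|---|---|---|
| 0 | 0 | 75% | 2.3% |
| 1% | 0.86 | 76% | 3.6% |
| 2% | 1.72 | 77% | 5.6% |
| 3% | 2.58 | 78% | 8.3% |
| 5% | 4.3 | 80% | 16.9% |

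As a share of non-responders converted, q = 1% is 0.01/0.25 = 4% and q = 5% is 0.05/0.25 = 20%.

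A boundary case shows the granularity: one subject with both eyes affected moves the interim count from 46/54 (continue) to 48/54 (stop for success).

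**Effect of counting them as non-responders.** If the 87.5% planning rate includes such eyes, the unaided rate is 0.875 − q and power falls:

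| q | Unaided rate | Power |
|---|---|---|
| 0 | 87.5% | 81.7% |
| 1% | 86.5% | 73.4% |
| 2% | 85.5% | 64.0% |
| 3% | 84.5% | 54.0% |
| 5% | 82.5% | 34.9% |

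Section 7.3 expects 90% and planned on 87.5%. If the 90% includes such eyes, a q of up to 0.90 − 0.875 = 2.5% still leaves power at 81.7% or more. If the planning rate already means the unaided rate, the rule costs no power.

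**The case against.** The strongest reply is that the documents are silent, and silence is not a statement that these eyes are successes. Several stronger readings are tempting, and the text does not support them.

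- **That 5.3 authorises exchange or laser enhancement.** It speaks of medical treatment and medications, so it bears directly on the drop case only. Exchange rests on 3.2.3, 4.3 and 6.3.1. Enhancement is merely not addressed.
- **That the per-protocol set carries the same problem.** This cannot be established. Treatment allowed by 5.3 does not look like a deviation, but the classes are left to the SAP.
- **That a drug-constricted pupil would go unnoticed.** Pupil diameter is scheduled only before surgery (Table A1). However, Tables A1 and A2 call for concomitant medications at every visit, and the Visit 5 slit-lamp examination rates iris and pupil as normal or abnormal.
- **That exclusion 11 clearly stops applying after surgery.** Unlike criterion 10, it carries no time limit. Its force after implantation is arguable.
- **That the bias must be upward.** It is upward for an eye that responds only because of the intervention. But Appendix B targets emmetropia within ±0.50 D, and an enhancement that removes residual myopia could reduce uncorrected near acuity. The net direction is not certain.

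The exchange example also has limits. Explant may end participation, and an eye with no Visit 5 data then leaves the full analysis set and is not counted as a success. The only ground for exchange described (6.1.1) is vault, not near acuity. An eye with a second study lens is arguably still a device result.

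All of this stands and narrows the claim. It does not remove the default: under 7.2.1 and 7.5 together, an eye with a passing Visit 5 result is a responder whatever preceded it, and discontinuation after explant is discretionary. That the exchange case is arguable is itself a reason to settle it in advance.

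**Conclusion.** The point holds as a gap with a default effect. The primary endpoint and the full analysis set ignore treatment received between implantation and Visit 5, so eyes helped to 20/40 by something other than the originally implanted lens would count as responders. This can inflate the responder rate; the documents do not show that it will.

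The decision rule is sensitive: at an unaided rate of 75%, a gain of one percentage point, less than one eye in 86, takes the chance of success from 2.3% to 3.6%, above the 2.5% limit. A gain of five points takes it to 16.9%. These figures assume independent eyes, an unaided rate exactly at the null, and shares for which the documents give no support either way. If no such eyes occur, nothing changes. This is a cheap improvement, not a flaw that invalidates the design.

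**What to change.** Leave clinical management and the permission in 5.3 as they are. In 7.2.1, 7.5 and the SAP, state that in the primary analysis, at interim and final, an eye with Visit 5 data is a non-responder if:
- it had a study-lens exchange before Visit 5;
- it had a secondary refractive procedure before Visit 5; or
- a pupil-constricting or presbyopia drop was in use at the Visit 5 near-acuity test.

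Identify these eyes from the concomitant medication records and the 6.3.1 reports. Neither source captures corneal procedures, so use source documents for those, and confirm from source that a recorded drop was in use at the test. Report the as-observed rate as a sensitivity analysis.

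The cost is a few sentences, a source check and one extra result line, with no added visits or subjects. The responder rate may be slightly less favourable, and power falls as tabulated if the planning rate includes such eyes. The loss should be small if they are rare, but it is not negligible at every assumed share.

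Eyes with no Visit 5 data after lens removal fall outside the full analysis set. They are a separate question that this rule does not settle.

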# 5.4 **Protocol Deviations**

The date of and reason for deviations will be documented in all cases. Significant or major protocol deviations impacting the safety of the subject or the integrity of the study must be reported by the Investigator to the EC immediately. Reporting of all other protocol deviations must adhere to the requirements of the governing EC.

Protocol assessments will continue until the end of the study, unless the protocol deviations put the subject at risk or the subject's condition requires that he/she be discontinued from the study.

# 6.0 ADVERSE EVENT REPORTING

Throughout the course of this study, all efforts will be made to remain alert to possible AEs. If an AE occurs, the first concern will be the safety of the subject, and appropriate medical intervention will be made. All ocular AEs and all SAEs (both ocular and non-ocular) will be reported by the Investigator in this study. Non-serious non-ocular AEs will not be documented in the eCRF. The collection of AEs begins at the time the subject completes the informed consent process to participate in the study.

All device-related AEs and SAEs reported in this study will be reviewed by the responsible Medical Monitor and forwarded to STAAR Complaint Handling department. In addition, all other events that meet the definition of a product complaint (i.e., device deficiency) will be evaluated and investigated in accordance with STAAR's complaint handling procedures.

Refer to Section 6.3.1 for instructions on events that require expedited reporting to the Sponsor.

#### 6.1 Definitions

#### 6.1.1 Adverse Event (AE)

According to EN ISO 14155, an **Adverse Event** is any untoward medical occurrence, unintended disease or injury, or untoward clinical sign (including abnormal laboratory findings) in subjects, users or other persons, whether or not related to the investigational medical device.

**NOTE 1:** This definition includes events related to the investigational device or the comparator.

NOTE 2: This definition includes events related to the procedures involved.

NOTE 3: For users or persons, this definition is restricted to events related to investigational medical devices.

Complications during phakic IOL surgery of the study eye must be reported as AEs in the corresponding eCRF section. A worsening of a pre-existing ocular condition during the study should be documented as an AE and evaluated according to the guidelines in Section 6.2.

Experience with intraocular surgery and the implantation of phakic IOLs has shown that some findings can be considered normal or expected events after these procedures. These findings may be considered normal or expected events after phakic IOL surgery, and need only be reported as AEs if the following criteria are met or exceeded:

- iritis/cells/flare if present at postoperative Visit 3 or later
- corneal edema if present at postoperative Visit 3 or later
- moderate or severe subjective visual disturbance (e.g., glare/halos) if present at postoperative Visit 4 or later (i.e., halo and glare in the early postoperative period is not reportable as an AE)
- elevated IOP if measuring  $\geq 30$  mmHg or  $\geq 10$  mmHg above baseline
- postoperative ocular event(s) if requiring a change in the standard postoperative medication regimen
- inadequate or excessive vault if ICL exchange is necessary to prevent permanent impairment, i.e., is sight threatening (if the lens is still performing as intended, variations in vault are not reportable as an AE)
- paracentesis to relieve elevated IOP if performed >1 week after implantation (paracentesis ≤ 1 week postoperative is not reportable as an AE)

#### 6.1.2 Adverse Device Effect (ADE)

According to EN ISO 14155 an Adverse Device Effect is an AE related to the use of an investigational medical device.

**NOTE 1:** This definition includes AEs resulting from insufficient or inadequate instructions for use, deployment, implantation, installation, or operation, or any malfunction of the investigational medical device.

**NOTE 2:** This definition includes any event resulting from use error or from intentional misuse of the investigational medical device.

#### 6.1.3 Device Deficiency

According to EN ISO 14155, a **Device Deficiency** is any inadequacy of the medical device with respect to its identity, quality, durability, reliability, safety or performance.

NOTE: Device deficiencies include malfunctions, use errors and inadequate labeling.

#### 6.1.4 Malfunction

According to EN ISO 14155, a malfunction is any failure of a medical device to perform in accordance with its intended purpose when used in accordance with the instructions for use or clinical study protocol or Clinical Investigation Plan (CIP).

#### 6.1.5 Serious Adverse Device Effect (SADE)

According to EN ISO 14155, a Serious Adverse Device Effect is any ADE that has resulted in any of the consequences characteristic of an SAE.

#### 6.1.6 Serious Adverse Event (SAE)

#### According to EN ISO 14155, a Serious Adverse Event is any AE that

- a) led to death,
- b) led to serious deterioration in the health of the subject, that either resulted in
  - 1) a life-threatening illness or injury, or,
  - 2) a permanent impairment of a body structure or body function, or
  - 3) in-patient or prolonged hospitalization, or
  - 4) medical or surgical intervention to prevent life-threatening illness or injury or permanent

impairment to a bod structure or body function,

c) led to foetal distress, foetal death or a congenital abnormality or birth defect.

**NOTE:** Planned hospitalization for a pre-existing condition, or a procedure required by the CIP, without serious deterioration in health, is not considered an SAE.

#### 6.1.7 Unanticipated Serious Adverse Device Effect (USADE)

According to EN ISO 14155, an **Unanticipated Serious Adverse Device Effect** is any Serious Adverse Device Effect (SADE) which by its nature, incidence, severity or outcome has not been identified in the current version of the risk analysis report.

